### 8.3.5 Analysis of Additional Efficacy Variables

#### 8.3.5.1 Analysis of Additional Spirometry Variables

Summary statistics for raw values and for change from baseline of the following spirometry measurements will be presented by treatment group at each visit:

- FEV1:
  - Absolute change from baseline in FEV1 (L)
  - Relative change from baseline in FEV1 (%)
  - Absolute change from baseline in percent predicted FEV1 (percentage points)
  - Relative change from baseline in percent predicted FEV1 (%)
- FVC:
  - Absolute change from baseline in FVC (L)
  - Relative change from baseline in FVC (%)
  - Absolute change from baseline in percent predicted FVC (percentage points)

- Relative change from baseline in percent predicted FVC (%)
- FEV1/FVC:
  - Absolute change from baseline in FEV1/FVC
  - Relative change from baseline in FEV1/FVC (%)
  - Absolute change from baseline in percent predicted FEV1/FVC
  - Relative change from baseline in percent predicted FEV1/FVC (%)

### **8.3.5.2 Analysis of Other CFQ-R Variables**

Descriptive summary statistics for raw values and for change from baseline of the CFQ-R non-respiratory domain scores will be presented by treatment group at each visit.

### **8.3.5.3 Analysis of Additional Variables for Pulmonary Exacerbations and Hospitalization**

The analysis period for all variables in this section will be the PEx analysis period.

#### **Pulmonary Exacerbations:**

In addition to the other secondary endpoint described in 8.3.3.2, PEx will be further analyzed as described below:

- Time-to-first event (in days):
  - Time-to-first PEx
  - Time-to-first PEx requiring hospitalization
  - Time-to-first PEx requiring intravenous (IV) antibiotic therapy
  - Time-to-first PEx requiring hospitalization or IV antibiotic therapy
- Number of events:
  - Number of PEx requiring hospitalizations through Week 52
  - Number of PEx requiring IV antibiotic therapy through Week 52
  - Number of PEx requiring hospitalization or IV antibiotic therapy through Week 52
- Duration of events:
  - Number of days with PEx through Week 52
  - Number of days with PEx requiring hospitalization through Week 52
  - Number of days with PEx requiring IV antibiotic therapy through Week 52
  - Number of days with PEx requiring hospitalization or IV antibiotic therapy through Week 52

#### **Hospitalization:**

- Number of events:
  - Number of planned hospitalizations for CF (i.e., antibiotic therapy) through Week 52

- Number of all unplanned hospitalizations for reasons other than antibiotic therapy for sinopulmonary signs/symptoms through Week 52
- Duration of events:
  - Number of days of planned hospitalizations for CF (i.e., antibiotic therapy) through Week 52
  - Number of days of all unplanned hospitalizations for reasons other than antibiotic therapy for sinopulmonary signs/symptoms through Week 52

#### **Analysis of PEx/Hospitalization Variables:**

For the time-to-event variables, the analysis time will be the number of days from the first dose date of study drug in the Treatment Period to the date of the first defined event during the PEx analysis period. A subject who does not experience the event during the PEx analysis period will be censored at the PEx analysis period end date for that event. The analysis of time-to-event will be based on the Kaplan Meier method; the corresponding plot will be presented.

For the number of events variables, subjects with multiple defined events during the PEx analysis period will be counted multiple times. A descriptive summary of the number of events along with the observed event rate will be provided.

The annualized duration of events for each subject will be the total number of days with the defined event times 48 weeks, divided by the total number of weeks in the study up to the end of the PEx analysis period. The annualized duration will be descriptively summarized.

### **8.4 Safety Analysis**

All safety analyses will be based on data from the TE Period for the Treatment Period for all subjects in the Safety Set for the Treatment Period, unless otherwise specified. Subjects will be analyzed according to the treatment they actually received in the Treatment Period, as applicable. Subjects receiving study drug from more than one treatment group will be allocated to the VNZ/TEZ/D-IVA group.

The overall safety profile of the study drug will be assessed in terms of the following safety and tolerability endpoints:

- Treatment-emergent adverse events (TEAEs)
- Clinical laboratory values
- ECGs
- Vital signs
- Pulse oximetry
- Ophthalmological examinations (for subjects <18 years of age on the date of informed consent)

Only descriptive analysis of safety will be performed, and no statistical testing will be performed.

### 8.4.1 Adverse Events

For analysis purposes, AEs will be classified as pretreatment AEs, TEAEs during the Run-in Period, TEAEs during the Treatment Period, or post-treatment AEs, defined as follows:

**Pretreatment AE:** any AE that occurred before the first dose date of study drug in the Run-in Period

**TEAE during the Run-in Period:** any AE that worsened (either in severity or seriousness) or that was newly developed on or after the first dose date of study drug in the Run-in Period through the end of the TE Period for the Run-in Period

**TEAE during the Treatment Period:** any AE that worsened (either in severity or seriousness) or that was newly developed on or after the first dose date of study drug in the Treatment Period through the end of the TE Period for the Treatment Period

**Post-treatment AE:** any AE that worsened (either in severity or seriousness) or that was newly developed after:

- the TE Period for the Run-in Period if the subject did not receive treatment in the Treatment Period
- the TE Period for the Treatment Period if the subject received treatment in the Treatment Period

For AEs with completely missing or partially missing start dates, if there is no clear evidence that the AEs started before or after study treatment, the AEs will be classified as TEAEs corresponding to the Treatment Period. Unless otherwise specified, TEAE refers to TEAE during the Treatment Period.

Details for imputing missing or partial start dates of adverse events are described in [Appendix](#) .

An overview of all TEAEs by treatment group and overall will be summarized in the following categories:

- Number of TEAEs (total number of TEAEs only)
- Subjects with any TEAEs
- Subjects with TEAEs by strongest relationship
- Subjects with TEAEs by maximum severity
- Subjects with TEAEs leading to study drug discontinuation (discontinuation of any study drugs)
- Subjects with TEAEs leading to study drug interruption (interruption of any study drugs)
- Subjects with Grade 3+ TEAEs
- Subjects with related TEAEs
- Subjects with serious TEAEs
- Subjects with related serious TEAEs
- Subjects with TEAE leading to death

The following summary tables of TEAEs will be presented by treatment group:

- All TEAEs
- TEAEs by strongest relationship
- TEAEs by maximum severity
- TEAEs leading to treatment discontinuation
- TEAEs leading to treatment interruption
- Grade 3+ TEAEs
- Related TEAEs
- Serious TEAEs
- Related serious TEAEs
- TEAEs leading to death

Summaries will be presented by MedDRA SOC and PT using frequency counts and percentages (i.e., number and percentage of subjects with an event). When summarizing the number and percentage of subjects with an event, subjects with multiple occurrences of the same AE or a continuing AE will be counted once, and only the maximum severity level will be presented in the severity summaries and the strongest relationship level in the relationship summaries.

Additional summary tables will be presented by treatment for TEAEs showing number and percentage of subjects:

- All TEAEs by PT

All AEs, including pretreatment AEs, TEAEs for all applicable periods, and post-treatment AEs, will be presented in an individual subject data listing based on the All Subjects Set. In addition, separate listings containing individual subject AE data for TEAEs leading to study drug discontinuation, TEAEs leading to study drug interruption, Grade 3+ TEAEs, all SAEs, and deaths will be provided, with a flag indicating the TEAE status for SAEs and deaths.

The following tables for the Run-in Period will be presented overall based on the Safety Set for the Run-in Period:

- An overview of TEAEs during the Run-in Period
- All TEAEs during the Run-in Period by SOC and PT

#### **8.4.2 Clinical Laboratory**

For the treatment-emergent laboratory assessments, the observed values and change from baseline values of the continuous hematology, coagulation, and chemistry results will be summarized in SI units at each visit by treatment group.

The number and percentage of subjects meeting at least 1 threshold analysis criterion event during the TE Period for the Treatment Period will be summarized by treatment group. The threshold analysis criterion shift from baseline will also be summarized for select laboratory parameters. The threshold analysis criteria are provided in [Appendix](#) .

For select liver function laboratory tests (alanine transaminase [ALT], aspartate transaminase [AST], alkaline phosphatase [ALP], and total bilirubin), a scatterplot of the maximum TE value versus the baseline value corresponding to xULN (upper limit of normal) will be presented. Further, a scatterplot of the maximum TE value of ALT and AST, separately, versus the maximum TE value of total bilirubin corresponding to xULN will also be presented by treatment group. For ALT, AST, and total bilirubin, box-and-whisker plots will be used to display raw values at each visit by treatment group.

Results of positive serum/urine pregnancy tests will be listed in individual subject data listings only. For the positive serum pregnancy listing, subjects with serum HCG which are abnormally high will be selected.

In addition, listings containing individual subject hematology, chemistry, coagulation, and urinalysis values will be provided. The listings will include data from both scheduled and unscheduled visits. A listing of subjects who meet the criteria of [(ALT>3xULN or AST>3xULN) and TBILI>2xULN] at any visit will be provided. This listing will include data from all visits (including unscheduled visits) and present values for ALT, AST, ALP, and total bilirubin.

#### **8.4.3 Electrocardiogram**

A summary of observed values and change from baseline values will be provided at each visit by treatment group for the following treatment-emergent ECG measurements (in msec): RR interval, PR interval, QT interval, QTcF interval, QRS duration, and heart rate (beats/minute).

The number and percentage of subjects meeting at least 1 threshold analysis criterion during the TE Period for the Treatment Period will be summarized by treatment group. The threshold analysis criteria are provided in [Appendix](#).

In addition, a listing containing individual subject ECG values will be provided. This listing will include data from both scheduled and unscheduled visits.

#### **8.4.4 Vital Signs**

For the treatment-emergent vital signs measurements, the observed values and change from baseline values will be summarized at each visit by treatment group. The following vital signs parameters will be summarized: systolic and diastolic blood pressure (mmHg), body temperature (°C), pulse rate (beats/minute), and respiratory rate (breaths/minute).

The number and percentage of subjects meeting at least 1 threshold analysis criterion during the TE Period for the Treatment Period will be summarized by treatment group. The threshold analysis criteria are provided in [Appendix](#).

In addition, a listing containing individual subject vital signs values will be provided. This listing will include data from both scheduled and unscheduled visits.

#### **8.4.5 Pulse Oximetry**

For the treatment-emergent pulse oximetry measurements, a summary of observed values and change from baseline values will be provided at each visit by treatment group for the percent of oxygen saturation.

The number and percentage of subjects with shift changes from baseline (normal/missing and low according to the reference range) to the lowest percent of oxygen saturation during the TE

Period for the Treatment Period will be summarized by treatment group. The reference range for normal oxygen saturation is specified as >95%, and ≤95% for low oxygen saturation.

#### **8.4.6 Ophthalmologic Examinations**

Ophthalmologic examination results will be presented in individual subject data listings only.

#### **8.4.7 Physical Examination**

Abnormal PE findings will be presented in individual subject data listings only.

#### **8.4.8 Supportive Safety Analysis**

##### **8.4.8.1 Adverse Events of Special Interest**

For this study, elevated transaminases, creatine kinase elevations, rash, cataracts, hypoglycemia, and neuropsychiatric events as determined by MedDRA PTs in [Appendix](#) are considered adverse events of special interest (AESI).

For AESI during the TE Period for the Treatment Period, the following categories will be summarized by treatment group:

- Subjects with events
- Subjects with events by maximum severity
- Subjects with events leading to treatment discontinuation
- Subjects with events leading to treatment interruption
- Subjects with related events
- Subjects with serious events
- Subjects with related serious events
- Subjects with events leading to death
- Duration of events
- Time-to-onset of first event

#### **8.5 Additional Analysis**

This section describes analysis of TSQM domains. Analyses of other exploratory assessments mentioned in the protocol may be described in a separate document. The description of analyses of additional variables of SwCl is also included.

##### **8.5.1 Analysis of TSQM Domains**

TSQM is a widely used generic measure of satisfaction with medication and has been demonstrated to be a valid and reliable measure of satisfaction in patients with CF. It consists of 14 items to form 4 domains: effectiveness (items 1, 2, 3), side effects (items 4, 5, 6, 7, 8), convenience (items 9, 10, 11), and global satisfaction (items 12, 13, 14). The score of each domain is a scaled score that ranges from 0 (least satisfied) to 100 (most satisfied). Scaled score for each domain can be calculated using the scale scoring algorithm^11.

**Absolute change from baseline in TSQM domains at Week 52** (only for subjects aged ≥12 years to <18 years at the date of informed consent) will be analyzed descriptively.

## **8.5.2 Analysis of Additional Variables for SwCl**

**Proportion of subjects with SwCl <60 mmol/L through Week 52 (pooled with data from Study 102)**: Analysis of this endpoint will be based on a GEE model similar to that for the proportion of subjects with SwCl <60 through Week 24 using the PFAS (8.3.2.2), with the addition of data from Week 36 and Week 52.

**Proportion of subjects with SwCl <30 mmol/L through Week 52 (pooled with data from Study 102)**: Analysis of this endpoint will be based on a GEE model similar to that for the proportion of subjects with SwCl <30 through Week 24 using the PFAS (8.3.2.2), with the addition of data from Week 36 and Week 52.

## **9 SUMMARY OF INTERIM AND DMC ANALYSIS**

### **9.1 Interim Analysis**

No interim analysis is planned for this study.

### **9.2 DMC Analysis**

The DMC will conduct planned safety reviews of study data as outlined in the DMC Charter. For the open session of each DMC meeting, selected tables will be presented for the overall treatment group based on blinded data. For the closed session, the analysis presentation will be by treatment group based on unblinded data (generated by the independent biostatistician).

## **11 LIST OF APPENDICES**

**Appendix A: Analysis Visit Windows for Safety and Efficacy Assessments**

**Table 11-1 Analysis Visit Windows for Safety and Efficacy Assessments**

Assessment	Visit 	Target Study Day	Analysis Visit Window  (in study days)
Safety Assessments			

 
• Pulse oximetry
 
• Serum chemistry
 
• Hematology (except HbA1c)
 
• Vital signs (excluding BMI, height, weight)
 
	Day 1 (Baseline)	1	≤1 Pre-dose
	Day 15	15	[1, 22]
	Week 4	29	(22, 43]
	Week 8	57	(43, 71]
	Week 12	85	(71, 99]
	Week 16	113	(99, 141]
	Week 24	169	(141, 211]
	Week 36	253	(211, 309]
	Week 52	365	(309, 379]
	Safety Follow-up	Not applicable	Use nominal visit
HbA1c (%)	Day 1 (Baseline)	1	≤1 Pre-dose
	Week 12	85	[1, 127]
	Week 24	169	(127, 267]
	Week 52	365	(267, 379]
Standard 12-lead ECG	Day 1 (Baseline)	1	≤1 Pre-dose
	Day 15	15	[1, 22]
	Week 4	29	(22, 43]
	Week 8	57	(43, 85]
	Week 16	113	(85, 141]
	Week 24	169	(141, 211]
	Week 36	253	(211, 309]
	Week 52	365	(309, 379]
		Safety Follow-up	Not applicable
Coagulation	Day 1 (Baseline)	1	≤1 Pre-dose
	Week 12	85	[1, 127]
	Week 24	169	(127, 211]
	Week 36	253	(211, 309]
	Week 52	365	(309, 379]
		Safety Follow-up	Not applicable
Efficacy Assessments			

 
• Spirometry (in-clinic)
 
• Height, weight, BMI, and z-scores
 
	Baseline	-	≤1 Pre-dose
	Day 15	15	[1, 22]
	Week 4	29	(22, 43]
	Week 8	57	(43, 85]
	Week 16	113	(85, 141]
	Week 24	169	(141, 211]
	Week 36	253	(211, 309]
	Week 52	365	(309, 379]
		Safety Follow-up	Not applicable

**Table 11-1 Analysis Visit Windows for Safety and Efficacy Assessments**

Assessment	Visit 	Target Study Day	Analysis Visit Window  (in study days)
Sweat Chloride	Baseline	-	≤1 Pre-dose
	Day 15	15	[1, 22]
	Week 4	29	(22, 71]
	Week 16	113	(71, 141]
	Week 24	169	(141, 211]
	Week 36	253	(211, 309]
	Week 52	365	(309, 379]
CFQ-R	Baseline	-	≤1 Pre-dose
	Week 8	57	[1, 85]
	Week 16	113	(85, 141]
	Week 24	169	(141, 267]
	Week 52	365	(267, 379]
TSQM	Baseline	-	≤1 Pre-dose
	Week 52	365	[1, 379]

Notes:

 Visit name for analysis purposes is used to report data in tables and figures.

 The analysis visit windows will be applied using the following rules for both scheduled and unscheduled visits:

- a. If no numerical measurement is available within a visit window, the measurement will be considered missing for the visit.
- b. If there is more than 1 numerical measurement available within a visit window, use the following rules:
  - i. The measurement closest to the target day will be used; or
  - ii. If there are multiple measurements with the same distance from the target day, the latest measurement will be used. If the latest measurement cannot be determined, and there are both scheduled and unscheduled visits, then the unscheduled visit will be selected.

 For measurements collected on the date of first dose of study drug in the Treatment Period, if it cannot be determined whether a measurement is before or after the first dose:

- a. Scheduled measurements will be treated as pre-dose observations.
- b. Unscheduled measurements will be treated as post-dose observations.

 For safety assessments, the Safety Follow-up analysis visit will be based on the nominal Safety Follow-up visit. If a subject does not have a nominal Safety Follow-up visit but has an early termination of treatment (ETT) visit with study day >379, then the ETT visit will be mapped to the Safety Follow-up analysis visit.

 For efficacy assessments, if a subject has a nominal Safety Follow-up visit with study day >379, then the nominal Safety Follow-up visit will be mapped to the Safety Follow-up analysis visit; else if a subject does not have a nominal Safety Follow-up visit with study day >379 but has an ETT visit with study day >379, then the ETT visit will be mapped to the Safety Follow-up analysis visit; else if there are multiple assessments with study day >379, then the earliest record will be selected as the Safety Follow-up analysis visit.

Derived Variables:

1. Age (in years) at first dose date and at nominal visits (for demographics, listings, and the calculation of [percent] predicted spirometry variables):

Obtain the age at informed consent (in days) in “yy, mm” format (e.g., 24 years, 6 months) from the Vital Signs (VS) page at the Screening Visit, and add 15.22 days to convert to days.

Obtain the informed consent date.

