**Table 3-2 Study VX20-121-103: Run-in Period, Treatment Period, and Safety Follow-up Visit**

Event/Assessment a	Run-in Period		Treatment Period b						ETT Visit c	Safety Follow-up Visit 28 (± 7) Days After the Last Dose of Study Drug (If Applicable) d	Comments
	Day -28 (± 1 Day)	Day -14 (Day -15 to Day -3)	Day 1	Day 15 (± 3 Days)	Weeks 4, 8, 12, 16 (± 5 Days)	Weeks 20, 28, 32, 40, 44, 48 (± 5 Days)	Weeks 24 and 36 (± 5 Days)	Week 52 (± 5 Days)			
Clinic visit	X	X	X	X	X e		X	X	X	X	See Section 9.1.8 for use of remote measures in extenuating circumstances.
Telephone contact						X					Assess the subject’s status, any AEs, concomitant medications, treatments, and procedures.
Inclusion and exclusion criteria review	X										Section 8
Randomization			X								Randomization may occur on either Day -1 or Day 1, after all eligibility criteria are confirmed (Section 9.1.3).
CFQ-R			X		Weeks 8 and 16		Week 24	X	X		Completed before the start of any other assessments on the day of the study visit (Section 11.5.3).

a All assessments will be performed before dosing unless noted otherwise.

b To enter the Treatment Period, conditions for entry must be satisfied (Section 9.1.3).

c If the subject prematurely discontinues study drug treatment, an ETT Visit should be scheduled as soon as possible after the decision to discontinue treatment (Section 9.1.5). Subjects who prematurely discontinue treatment during the Run-in Period will complete an ETT Visit and Safety Follow-up Visit, as applicable. Subjects who prematurely discontinue study drug treatment during the Treatment Period should continue to complete all scheduled study visits for assessments following completion of the ETT Visit (and Safety Follow-up Visit, if applicable).

d The Safety Follow-up Visit is required for all subjects, unless otherwise specified (Section 9.1.4). For subjects who complete an ETT Visit 3 weeks or later following the last dose of study drug, the ETT Visit will replace the Safety Follow-up Visit, and a separate Safety Follow-up Visit will not be required (Section 9.1.5).

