#### **Baseline value:**

For all safety endpoints:

- Unless otherwise specified, baseline will be defined as the most recent non-missing measurement (scheduled or unscheduled) collected before the first dose of study drug in the Treatment Period (i.e., the Day 1 Visit).

For all efficacy endpoints:

- Except for SwCl, baseline will be defined as the pre-dose Day 1 value. If the pre-dose Day 1 value is missing, the most recent pre-dose, non-missing value on or after the Day -14 visit, including unscheduled visits, will be used as baseline.
- For SwCl, baseline will be defined as the average of the two most recent pre-dose, non-missing values on or after the Day -14 visit, including unscheduled visits. If only 1 non-missing value is available during this interval, the available value will be considered as baseline.

**Absolute change** from baseline will be calculated as post-baseline value - baseline value.

**Relative change** from baseline will be calculated as (post-baseline value - baseline value)/baseline value.

The **Treatment-emergent (TE) Period for the Run-in Period** will be from the first dose date of study drug in the Run-in Period to (1) the first dose date of study drug in the Treatment Period for subjects who complete the Run-in Period and continue to the Treatment Period, or (2) 28 days after the last dose date of study drug in the Run-in Period or to the completion of study participation date, whichever occurs first, for subjects who do not continue to the Treatment Period (e.g., subjects who do not meet the conditions to enter the Treatment Period).

The **TE Period for the Treatment Period** will be from the first dose date of study drug in the Treatment Period (VNZ/TEZ/D-IVA or ELX/TEZ/IVA) to 28 days after the last dose date of study drug in the Treatment Period or to the completion of study participation date, whichever occurs first.

The **PEx analysis period through Week 52** will be from the first dose date of study drug in the Treatment Period to the last efficacy assessment, which may be collected up to the Week 52 Visit or the earlier of Day 365 and the completion of study participation date if a subject does not have the Week 52 Visit.

**Unscheduled visits:** Unscheduled visit measurements will be included in analysis as follows:

- 1) In scheduled visit windows per specified visit windowing rules
- 2) In the derivation of baseline and last on-treatment measurements

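### The SAP's nearest-to-target rule could let an unscheduled clinic spirometry replace a valid, in-window scheduled Week 16 or Week 24 value; the effect is small and the remedy is a sort-order change

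*SAP*

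**What the plan says.** SAP Section 8.1 brings unscheduled measurements into the analysis ("Unscheduled visit measurements will be included in analysis as follows"), and its first route is "In scheduled visit windows per specified visit windowing rules".

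The windowing rules are in SAP Appendix A, Table 11-1, note 2. Their scope is explicit: "The analysis visit windows will be applied using the following rules for both scheduled and unscheduled visits". Where a window holds more than one value, note 2.b works in three steps:

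1. "The measurement closest to the target day will be used".
2. "If there are multiple measurements with the same distance from the target day, the latest measurement will be used".
3. If the later one cannot be identified "and there are both scheduled and unscheduled visits, then the unscheduled visit will be selected".

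For in-clinic spirometry, the Week 16 window has target Day 113 and runs over Days 86 to 141. The Week 24 window has target Day 169 and runs over Days 142 to 211. Protocol Table 3-2 allows each of these visits to take place up to 5 days either side of its target.

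The primary variable averages Weeks 16 and 24 only (SAP 8.3.1.1), and the protocol restricts the primary analysis to clinic spirometry (Section 12.3.3.1). Neither document gives the scheduled value priority or plans a scheduled-visits-only sensitivity analysis. The one supplementary analysis of the primary endpoint (SAP 8.3.1.4) concerns treatment discontinuation and use of non-study CFTR modulators.

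**The concern.** A scheduled value has a date fixed in advance. An unscheduled value may have a date that depends on how the subject is doing. Using an unscheduled value to fill a gap is reasonable. Letting it displace a valid, on-time scheduled value is a different step, because it could make the choice of measurement depend on the outcome.

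For example, a Week 24 visit on Day 173 is within the protocol window. If the subject also had an unscheduled clinic test on Day 168, that test is 1 day from target against 4, so it becomes the Week 24 value and the scheduled one is not used.

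The endpoint rests on two visits, so each carries half the weight. If displacement by low values were more frequent in one arm, the treatment difference would shift. The same confidence interval supports a superiority claim when its lower bound exceeds 0 (SAP 8.3.1.3), and there the 3-point margin gives no cushion.

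**Working it through.** **1. The plan's own figure.** Inputs from SAP 6.2.1: 275 per arm, 10% drop-out, SD 8, margin 3, true difference 0, 1-sided 0.025.

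- Evaluable per arm: 275 × 0.9 = 247.5.
- SE = 8 × √(2/247.5) = 0.72.
- Power = Φ(3/0.719 − 1.96) = Φ(2.21) = 98.7% (98.6% with the noncentral t).

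This agrees with the stated figure of more than 95%. It does not depend on the windowing rule.

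**2. How often the rule can displace a compliant visit.** Let the scheduled visit fall k days from target, with k from −5 to +5. An unscheduled test on another day is selected if it is nearer the target, or equally near and later. The count is the same for both visits.

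| Scheduled visit | Displacing days |
|---|---|
| 5, 4, 3, 2, 1 days early | 10, 8, 6, 4, 2 |
| on target | 0 |
| 1, 2, 3, 4, 5 days late | 1, 3, 5, 7, 9 |

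- A visit 5 days early can be displaced by a test on Days 109–118 (Week 16) or 165–174 (Week 24).
- A visit 5 days late can be displaced by a test on Days 109–117 or 165–173.
- If k is spread evenly over ±5, the average is (30 + 0 + 25)/11 = 5.0 days per visit.
- Same-day tests are additional to this count. Even a visit on the target day can lose to a later test that day, or to an unscheduled record when the order is unknown.

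**3. Share of subjects affected.** The documents give no rate of unscheduled clinic spirometry. Assume 0.5 to 2 condition-prompted tests per subject-year, spread evenly over time. The expected share with one of the two values replaced is 2 × (5/365) × rate:

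- 0.5 per year: 1.4%
- 1 per year: 2.7%
- 2 per year: 5.5%

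**4. Shift in the treatment difference.** Assume also that a displacing value lies 5 to 15 points below the scheduled one. Then

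shift = 2 visits × 0.5 × (5/365) × drop × (difference in rates between arms).

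- Equal rates: 0.
- 0.5 v 1 per year, 5-point drop: (5/365) × 5 × 0.5 = 0.03.
- 0.5 v 1 per year, 15-point drop: (5/365) × 15 × 0.5 = 0.10.
- 1 v 2 per year, 5-point drop: (5/365) × 5 × 1 = 0.07.
- 1 v 2 per year, 15-point drop: (5/365) × 15 × 1 = 0.21.

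**5. Consequence at the extreme (0.205 before rounding, SE unchanged).**

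- Against the test arm: power = Φ((3 − 0.205)/0.719 − 1.96) = 97.3%, down from 98.7%.
- In its favour, at a true difference of −3: 1-sided error = 1 − Φ(1.96 − 0.205/0.719) = 4.7%, up from 2.5%.

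**The case against.** The rule is prespecified and selects on date, not on value or arm. The trial is double-blind, and the SAP is to be final before database lock and unblinding (SAP Section 3). Choosing the value nearest the target also suits a visit-specific estimate. All of this stands, and it is why the expected bias is zero unless displacement differs between arms.

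Four stronger readings are tempting, and the documents do not support them.

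- **That illness-triggered values do enter the endpoint through this rule.** No section says why unscheduled spirometry is done. Protocol 10.7.1 mentions spirometry related to adverse event reporting, without saying that it is unscheduled or done in clinic. Protocol 11.5.4.1 lists a 10% fall in lung function as an exacerbation sign but orders no extra test. Protocol 11.5.1 sends all spirometry to central quality review, so a repeat after a poor test is an equally open reason, and that repeat could be the better value.
- **That unscheduled tests are less standardised.** The pre-bronchodilator and predose requirements in Protocol 11.5.1 are not confined to scheduled visits. That section also accepts a post-bronchodilator scheduled test when a subject forgot to withhold.
- **That the problem extends to sweat chloride and CFQ-R.** The rule covers them, but nothing in the documents suggests that they are collected because a subject is unwell.
- **That scheduled-first selection would keep illness values out.** Exacerbation is not an intercurrent event (SAP 8.3.1.2), so values affected by illness can enter through scheduled visits anyway.

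The preference for the unscheduled record in ties is also narrow. Equal distances on different dates go to the later test, so in practice this preference applies only to same-day tests of unknown order.

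An unconditional scheduled-first rule would also go too far. In windows of 56 and 70 days, a scheduled value far from target need not be better than a nearer unscheduled one.

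**Conclusion.** The gap is real but small. As written, the rule could replace a valid scheduled Week 16 or Week 24 spirometry obtained within ±5 days, and nothing else in the plan undoes this. Whether that makes the endpoint depend on health status rests on an assumption about why unscheduled tests are done.

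The 0.03 to 0.21 point range rests on assumed test rates, a two-fold difference between arms and drops of 5 to 15 points. Its direction is unknown. The upper end needs the highest rates and the largest drop together, and it is still 0.205/0.719 = 0.29 of one standard error and 7% of the margin (0.205/3). A reader should not infer that the non-inferiority conclusion is in danger. This is a free improvement, best made while the study is blinded, because a later change in which reading counts would look post hoc.

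**What to change.** For in-clinic spirometry, amend SAP Table 11-1 note 2.b as follows:

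- If a valid scheduled-visit measurement (accepted by central quality review) exists within the protocol's ±5-day visit window, use it.
- Otherwise, apply the existing nearest-to-target rule to all measurements in the analysis window.
- Resolve same-day ties of undetermined order in favour of the valid scheduled value.

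The number of displacing days for a valid scheduled value within ±5 days then falls from an average of 5.0 per visit to 0. Unscheduled values still fill gaps, so no subject loses a visit value, and the planned power is unchanged. The cost is a few lines of SAP text and a change of sort order in the derivation, documented in a SAP amendment before database lock.
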